### **5.5** Standards Applied:

U. S. EPA Good Laboratory Practice Regulations (40 CFR 160); 40 CFR 26 subparts K and L; FIFRA § 12(a)(2)(P); California State EPA Department of Pesticide Regulation study monitoring (California Code of Regulations Title 3, Section 6710).

#### 6 INVESTIGATIONAL AND TEST MATERIAL CONTROL:

#### **6.1** Test Substance:

# **6.1.1** Description of the Test Substance

Formulations containing EMD's proprietary IR3535-based repellent will be tested. IR3535 is a US/EPA-registered repellent active ingredient, Ethylbutylacetylamino-propionate. It is the active ingredient in numerous registered commercial personal insect repellents marketed worldwide, including the US/EPA-registered Avon Bug Guard line. The three test formulations are Lotion WV29-01-9N (lot # M17345), Aerosol EUS26-16-9N (lot # M17346), and Spray EUS26-15-9N (lot # M17279). They are "pending products" to be submitted to EPA for registration as insect repellents. Details of the test formulations are appended.

#### **6.1.2** Trade Name:

#### **TBD**

### **6.1.3** Dosage Form:

Liquid applied to exposed skin.

#### **6.1.4 Dose:**

Determining dosage is a main objective of this study. Dosage for repellency testing will be the mean of the subject means determined for each product in the dosimetry portion of this study. Dosage will be measured in weight and reported by weight and volume.

### **6.1.5** Manufacturing Site:

ACCRA PAC Inc., Elkhart Indiana USA.

# **6.1.6 Test Material Storage During Study:**

Prior to application, test materials will be stored indoors, at room temperature and away from direct sunlight or direct sources of moisture. Storage will be at Carroll-Loye Biological Research.

# **6.1.7 Test Material Safety:**

EPA regulates use of inert ingredients (also termed "other" ingredients) by toxicology profiles in animal tests and by their inclusion in EPA lists of "approved" other ingredients. Ingredients on lists 4a or 4b are considered relatively safe for all uses. The ingredients in the proposed insect repellent formulations are mainly on lists 4a or 4b with a few ingredients on list 3 because of ocular irritation potential (e.g., alcohols). EPA normally regulates the presence of materials on list 3 by labeling to avoid contact with eyes and to prohibit application by children. The other ingredients in the test formulations are

commonly used in marketed products for application to human skin as components of cosmetic and drug formulations.

The insect repellent products proposed for registration have all been tested in animals for potential for oral and dermal toxicity, dermal inhalation, ocular and dermal sensitization potential; studies on droplet size of spray and aerosol products showed that there was little if any potential for inhalation exposure. These studies will be submitted and reviewed by EPA as part of the registration process. The results of these tests showed a low order of toxicity characteristic of similar tests on the "neat" active ingredient cited by EPA in approvals of this product for application on humans. The IR3535 active ingredient has an extensive, positive safety record of in consumer use.

MSDS documentation is the same as that submitted with the previous version of this protocol.

### **6.1.8 Test Material Composition and Stability:**

The Test Material formulations are typical of topical cosmetics and insect repellent products marketed to consumers. They were produced under Good Manufacturing Practices (GMPs) with records available to EPA. Production of these insect repellents involves only simple mixing of the ingredients and does not involve chemical reactions that can be an issue with other pesticide products; ingredients are non-reactive as documented in storage stability studies that are required for submission to EPA as part of the registration process.

Test materials were produced in February 2006. They were couriered to Carroll-Loye Biological Research on 7 April 2006, with Chain-of-Custody documented. Since that time they have been stored at the Carroll-Loye Offices at in a closed cabinet at room temperature (20-24°C). The composition and content of active ingredients in the products used for the proposed efficacy studies will be confirmed by analytical methods prior to and following human subject efficacy testing. Storage stability testing is also being conducted. The EPA has extensive experience with enforcing requirements for such tests based upon their history

with similar products applied to humans and EMD intends to provide any requested information as appropriate to safety and efficacy issues.

### **6.2.** Negative Control:

### **6.2.1** Description of the Negative Control

The negative control is untreated for both dosimetry and repellency assays.

### **6.2.2** Rationale for Employing a Negative Control

Repellent efficacy can only be measured in the presence of biting mosquitoes. In addition, the duration of repellency recorded is likely a function of the number of host-seeking mosquitoes active during the study. The US/EPA uses a standard minimum rate of mosquito attack on untreated subjects to insure that the repellents under study are sufficiently challenged to provide meaningful data. Traditionally the measure rate is termed the 'ambient biting pressure'. We adopt that value, but use LIBes ('Lites with Intent to Bite') rather than bites. A mean study LIBe rate of ≥ 1 LIBe per untreated (negative control) lower leg or lower arm per 1 minute is required.

We take several precautions to minimize the probability to untreated control subjects receive any bites (see §§ 5.4, 8.2, 8.3.1, 8.4.1, 10.3.6). Recognizing that individual subjects differ in their inherent attractiveness to mosquitoes, US/EPA science reviewers have recommended that we use two untreated control subjects for this study in order to improve the likelihood of sampling ambient biting pressure in a representative fashion, while still exposing a very small number of untreated subjects to risks from foraging mosquitoes. Having separate untreated subjects also avoids the problem of interaction between treated an untreated limbs that may obtain when subjects serve as their own simultaneous controls. In reviewing an earlier version of this protocol in May 2006, the California Department of Pesticide Regulation asked for use of a single negative control, but compromised at two such subjects based on the position of the US/EPA. The prospect of

receiving approval to use more untreated control subjects is probably small in this case.

There is no control in which each formulation matrix without the repellent active is tested. There is no a priori basis for anticipating significant repellent activity in the matrices, and the study objective is to examine efficacy of the end products. The question of whether there is interaction between matrix and active is external to that objective. Accordingly, the added risk of including additional subjects testing matrix-only formulations cannot be justified.

### **6.3** Test Arthropod Species:

Testing will be conducted with all or some of wild *Aedes vexans*, *Ochlerotatus melanimon*, *O. taeniorhynchus*, and *Culex pipiens* mosquitoes, and possibly other mosquito species that occur in the same habitats. Mosquito specimens will be collected from untreated control subjects during testing and identified in the laboratory using taxonomic keys and stereomicroscopy in the laboratory.

#### 7 STUDY SCHEDULE:

1

### 7.1 Proposed Date of Initiation:

TBD, within one year of IRB approval.

#### **7.2** Schedule of Events:

TBD

Test day	Date	Activities
-302 7	ΓBD	Begin subject recruitment. Introduce subjects to test plan and procedures; explain compensation; review subject rights and consent forms; option to sign consent forms in order to participate; measure limb surface areas; determine individual dosage values.

Prepare individual dosages for application.

Meet with subjects to review day plan and safety procedures. Travel to field site. Review safety and data collection procedures. Administer repellent, commence repellency data collection. Monitor subject safety, comfort, comportment, compliance with data collection protocol.

### **7.3** Proposed Date of Completion:

Experimental Completion Date (Test Day 1): TBD. Final Report Completion Date: TBD.

#### **8 STUDY DESIGN:**

### **8.1** Treatment Groups:

There are two experimental groups, namely 1) a 'treated' group of subjects treated with the test products, of which there are three formulations, and 2) an untreated ('negative') control group.

# 8.2 Experimental Design:

The experiment will be treated as a partially randomized, experimenter and subject-blinded trial. However, control subjects will be chosen only from among individuals that are experienced in field biology or entomology. Whether arms, legs or both are tested at a given site will depend on the species of mosquitoes present and their behavior. That decision will be made by the Study Director based on visits to the field sites prior to data collection.

# **8.3** Randomization Procedures for Repellent Efficacy Testing:

# 8.3.1 Allocation of subjects to treatment groups:

Subjects will be assigned to the treatment (but not negative control) groups on the basis of a randomly assigned subject number. Subjects will be assigned a treatment based on their subject number and the treatment allocation table, which follows. Treatments will be balanced between arms and legs if both limbs are used. Negative control subjects will be selected exclusively from among experienced personnel.

#### **8.3.2** Treatment allocation table:

Materials will be distributed among subjects as tabulated below. (Alternatively, pending consultation with US/EPA, the Pump and Aerosol treatments, which have the same concentration of the active ingredient and which will be very similar to one another after their carrying material evaporates, may be tested simultaneously on alternate limbs of the same subjects. Doing so would reduce the absolute subject exposure by 10 individuals. To preserve subject security from biting mosquitoes, limbs would be exposed one at a time.) Two personnel who will monitor ambient biting pressure with untreated limbs are also listed to clarify the design of the test.

Subject	t Lotion	Pump	Aerosol	Untreated
1	Left limb			
2	Right limb			
3	Left limb			
4	Right limb			
5	Left limb			
6	Right limb			
7	Left limb			
8	Right limb			
9	Left limb			
10	Right limb			
11		Left limb		
12		Right limb		
13		Left limb		
14		Right limb		
15		Left limb		
16		Right limb		
17		Left limb		
18		Right limb		
19		Left limb		
20		Right limb		
21			Left limb	
22			Right limb	
23			Left limb	

24		Right limb	
25		Left limb	
26		Right limb	
27		Left limb	
28		Right limb	
29		Left limb	
30		Right limb	
31			Left limb
32			Right limb

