#### 9.1.5 Identification method and records retention:

Subjects will initially be identified by first and last name, and assigned a unique number for purposes of this study. Individual data will be entered into the computer for retention and analysis with reference to individual number, not name. Records relating individual names to individual numbers will be retained separately. The Study Director will retain records indefinitely. Subjects may obtain their own records from the Study Director.

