# 9.2 Blinding of Study:

# 9.2.1. Extent of the Blinding:

The types of Test Materials and their identities will be evident to subjects as they apply them during the dosimetry portion of the study. During the repellency portion of the study, subjects will be blinded to the exact treatments they receive although some may note differences between the lotions and the clear liquids in the repellency potion of the study. The Study Director will be blinded to the identity of individual treatments until the conclusion of data evaluation.

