### 11.2 Replicates per Treatment:

For dosimetry, there will be 12 treated subjects, each serving as their own untreated control, testing each of the three repellent formulations. For repellency testing, there will be 10 subjects treated with each test repellent and two serving as untreated controls for repellency testing at each of two sites.

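### The uncoded allocation table makes the subject number a treatment key, which defeats the stated blinding of the Study Director and analyst

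*Combined protocol and SAP*

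**What the plan says.** **Allocation.** Section 8.3.1 places treated subjects in groups "on the basis of a randomly assigned subject number" and continues: "Subjects will be assigned a treatment based on their subject number and the treatment allocation table, which follows". Section 8.3.2 opens with "Materials will be distributed among subjects as tabulated below" and prints the table under the product names. Subjects 1-10 receive lotion, 11-20 pump, 21-30 aerosol, and 31-32 are untreated. Limb side alternates left and right with odd and even numbers.

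**Blinding.** Section 8.2: "The experiment will be treated as a partially randomized, experimenter and subject-blinded trial". Section 9.2.1: "The Study Director will be blinded to the identity of individual treatments until the conclusion of data evaluation". For subjects the claim carries a stated limit: "subjects will be blinded to the exact treatments they receive although some may note differences between the lotions and the clear liquids". Section 9.2.2 describes the method: a researcher codes the materials and the forms by treatment, and the Study Director opens the codes once the analysis is complete.

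**Data.** Section 9.1.5: "Individual data will be entered into the computer for retention and analysis with reference to individual number, not name". The list linking names to numbers is kept apart from the data, but the Study Director retains the study records.

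**The concern.** The allocation rule and the blinding claim work against each other. The Study Director conducts the study under this protocol and completes the analysis on data identified by number. A fixed, named map from number to product sits in the same document. Nothing in the protocol withholds the table from anyone, or replaces the allocation number with another identifier before analysis.

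This matters because the endpoint rests on judgement. A lite with intent to bite (LIBe) is defined in 5.1 by proboscis contact while the mosquito has stopped moving. Subjects report it and technicians record it (10.3.6), and it counts towards CPT only if a confirmation rule is met (11.3.2). Someone who knows the product could handle a doubtful record differently without meaning to. Expectation also has something to work on: Appendix 1 lists 20% active ingredient in both sprays and 10% in the lotion. A study report that repeats the blinding claim would be contradicted by its own protocol.

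**Working it through.** **Inputs.** The table (8.3.2); the group sizes (9.1.3, and 11.2: "there will be 10 subjects treated with each test repellent and two serving as untreated controls for repellency testing at each of two sites"); the indexing of the data (9.1.5); the coding step (9.2.2); the conceded limit on subject blinding (9.2.1).

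**Step 1: reproduce the plan's counts.** The table gives 10 lotion, 10 pump, 10 aerosol and 2 untreated, 32 in all. This agrees with 9.1.3 and 11.2. Each product has 5 left and 5 right limbs, and the untreated pair has one of each.

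**Step 2: how much does the number reveal?** Take the chance of naming a treated subject's product correctly.

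- Number plus the printed table: 30/30 = 1.
- Number plus a concealed random list with 10 per product: 10/30 = 0.33. There are 30!/(10! × 10! × 10!) = 5,550,996,791,340 such lists.
- Concealed list, but an observer recognises lotion by sight and cannot tell the two clear liquids apart: (10 + 20 × 1/2)/30 = 20/30 = 0.67.

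For an observer who can already recognise the lotion, concealment therefore moves the figure from 1 to 0.67. All of that difference comes from pump versus aerosol, where a correct call falls from certain to 1/2.

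**Step 3: does the coding in 9.2.2 close the route?** Coding hides the product name on a syringe or form. It does not change the number. If each product has one code, that code attaches to a single run of ten consecutive numbers. One subject number together with the table then decodes the product for all ten. The coding protects only someone who lacks either the number or the table.

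**Step 4: who has both?**

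- *Study Director or analyst:* has the protocol, and analyses data indexed by number. The claim in 9.2.1 fails on the face of the text.
- *Subjects and field recorders:* nothing says that they are given the table, and nothing says that it is kept from them. The sample field form (Appendix 2) asks for a name and a test number and has no labelled subject-number field. Their blinding is unverified, but it is not shown to be absent.

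**Step 5: is the table number the data number?** The table has 32 slots. The study has 2 × 30 = 60 treated places and 2 × 2 = 4 untreated places, and 9.1.6 enrols three extra subjects. The number that 9.1.5 calls unique within the study cannot equal a 1-32 slot for everyone. The numbering would have to restart at each site, or a second identifier would have to exist. The documents do not say which. The count of 30 of 30 per site assumes that the table number travels with the data, and 60 of 60 further assumes that the same table serves both sites.

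**Step 6: leverage on the endpoint.** CPT is resolved in 15-minute steps and averaged over 10 subjects, so moving one subject by one step shifts a product mean by 15/10 = 1.5 minutes. This shows how sensitive the mean is to a single call. It is not an estimate of bias, and the documents offer no basis for one.

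**The case against.** The strongest reply is that the protocol contains a real masking step. Materials and forms are coded, and the people who make and record LIBe calls are not shown to hold the table. That stands. A reader might infer that the trial has no blinding at all; the text does not support this for subjects and recorders.

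A reader might also infer that assignment in blocks makes the allocation non-random. It does not: the subject number is itself randomly assigned (8.3.1), so a fixed map from number to product still gives a random allocation. What remains is that the plan does not say how numbers are generated or concealed, so a person assigning them with the table to hand could foresee the product.

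Nor do the documents show that product is confounded with time of dosing or with partner. Section 10.3.6 says only that subjects work in pairs, and no section says that dosing or pairing follows number order. Section 9.1.6 does not say who calls in alternates, so it cannot be said that an unblinded Study Director controls replacement.

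Finally, 11.3.2 plans a mean, standard deviation and confidence interval for each product and no formal comparison of products on repellency. All treated subjects receive an active product, and pump and aerosol have the same concentration. This limits the likely consequence. It does not remove the contradiction over the Study Director, and a per-product mean can still be affected by how its records are read.

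**Conclusion.** The concern holds in a limited form. As written, the plan does not deliver the blinding of the Study Director and analyst that 8.2, 9.2.1 and 9.2.2 state. It leaves the blinding of subjects and recorders at risk, chiefly for pump versus aerosol. All 30 treated assignments per site can be deduced, provided that the table numbers are those carried in the data. Complete absence of blinding, non-random allocation and confounding with dosing order are not established, and the effect on CPT cannot be quantified from the documents. The point should be corrected before the field trials, because the remedy is cheap and the endpoint depends on judgement.

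**What to change.** 1. Replace the printed mapping in 8.3.2 with a blank template.
2. Have the coding researcher already provided for in 9.2.2 generate a concealed random list for each site. Blocks of six, with one left and one right limb per product, fill the 30 places in 30/6 = 5 blocks. They keep 10 per product and 5 left and 5 right (5 × 2 = 10; 5 × 1 = 5 per side). Even with this restriction there are (6!/(2! × 2! × 2!))^5 = 90^5 = 5,904,900,000 possible product sequences, and the number alone gives a chance of 2/6 = 1/3.
3. That researcher holds the list until the data are locked. State in 8.3.1 how numbers are assigned and that the assigner does not see the list.
4. State in 9.1.5 that the analysis data use identifiers that do not map to treatment, and how these relate to the allocation numbers at each site.
5. If the alternate-limb option in 8.3.2 is taken up (pump and aerosol on the same subjects, 10 fewer subjects), write a matching list for that design.

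The cost is one short program, a sealed list and a text amendment, with no added staff or subjects. If the sponsor prefers to keep the printed table, the blinding claims in 8.2 and 9.2 should be withdrawn or qualified to what the plan delivers.

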### 8.4. Conditional Boundaries or Limits of Study

#### **8.4.1.** Ambient 'Lite with intent to bite' Pressure:

A mean study LIBe ('Lite with Intent to Bite') rate of  $\geq 1$  LIBe per untreated (negative control) lower leg or lower arm per 1 minute is required. No more than 10% '0' values for individual exposure periods are permitted. Ambient LIBe pressure is measured from continuous exposure during 1-minute exposure periods commencing once every 15 minutes, beginning at the onset of data collection. Negative control subjects are attended by two assistants who use mechanical aspirators to remove all mosquitoes that LIBe before biting commences.

# 8.5. Monitoring of Environmental Conditions During the Study

Records will be made of environmental conditions (temperature, relative humidity, wind speed, light intensity and precipitation (presence/absence and general rate/quality) at approximately one-hour intervals throughout the course of data collection.

#### **9 STUDY PROCEDURES:**

# 9.1 Test Subjects:

#### 9.1.1 Inclusion criteria:

9.1.1.1	Age:	18-55 years
9.1.1.2	Sex:	Male/female
9.1.1.3	Race:	Any race

- 9.1.1.4 Written consent (see 9.4, below).
- 9.1.1.5 Language: Speak and read English

#### 9.1.2 Exclusion criteria:

- 9.1.2.1 Known to be hypersensitive to mosquito bites or exhibiting hypersensitivity during test 9.1.2.2 Known to be sensitive or showing sensitivity to any of the test product ingredients after application. 9.1.2.3 Poor physical condition. 9.1.2.4 Unwilling to submit to brief query about personal condition. 9.1.2.5 Use of insect repellent within three days preceding the study. 9.1.2.6 Unwilling to refrain from use of perfumed products, alcoholic beverages or smoking after 9 PM the evening preceding the test and throughout the test. 9.1.2.7 Known to be pregnant or lactating. Pregnancy will be self-checked by each female volunteer on the morning of the repellent test using an OTC test kit provided by the Study Director. Results of each such test will be immediately verified by direct inspection by a female technician trained to make that assessment. Only volunteers scored as nonpregnant will be allowed to participate.
  - 9.1.2.8 Inability to deliver the test materials to own left and right limbs.
  - 9.1.2.9 Student or employee of the Study Director.
  - 9.1.2.10 Do not regularly spend time in outdoor settings.

# 9.1.3 Number of Subjects and Rationale for Sample Sizes:

Dosimetry: 12 subjects per treatment formulation (namely lotion, pump spray, aerosol). Repellent efficacy: 10 subjects per treatment formulation and 2 untreated control subjects. Each subject is a replicate.

The number of subjects is chosen as a compromise between several conflicting factors. In the absence of clear means of estimating the distribution of outcome values, it is difficult to predict an ideal sample size. From a strictly scientific standpoint an appropriate response under such circumstances is to increase size, but ethical and economic consideration demand the opposite in the present study, particularly during the repellency phase.

The US/EPA has historically required a minimum of six subjects. Given that test repellents are nearly certain to exhibit greater than zero efficacy, and that testing is conducted under adequate ambient biting pressure, it is nearly certain that no untreated subjects will register fewer or later LIBes than any treated subjects. As a result, from the standpoint of statistical **power**, six treated and one untreated subject are sufficient to demonstrate a significant treatment effect at P<0.05. In the same vein, six is often regarded as a statistically sufficient sample for an observation subset because the increment in the confidence of means estimate begins to drop off sharply at that point. Notably, under the historical guidelines, there seem to have been few problems with EPA registering repellents that commonly fail to meet their labeled performance specification.

The main scientific risk of using a very small sample is that the probability of over-representing subjects inherently unattractive to mosquitoes is rather large. Note, however, that for US/EPA registration purposes, the test for mosquito repellency is conducted twice, once in each of two ecologically different habitats. In our experience, the subjects in one test normally do not participate in the other (due to large geographic distances between sites). In addition, two negative controls are used for a more robust baseline comparison. Those facts decrease the probability of such sampling error substantially.

However, further considerations indicate that a somewhat larger sample would be superior. Note that the draft EPA guidelines state that the response variable, 'Time to First Confirmed Bite' (or LIBe in this study) is calculated as the average duration for all treated subjects. There is no consideration of variation. In any given study, increasing the number of treated subjects to 10 will improve the probability of estimating the population mean accurately.

The 95% confidence interval computation is useful for assessing the certainty of a means estimate, and for normal probability density function that interval is ±1.96 standard error of the mean. The normal density function is part of the exponential family of density functions, and in this study we anticipate that the distribution of Times to First Confirmed LIBe will be truncated toward the origin. However, available mean and variance data on IR3535 performance (Cilek et al. J. Amer. Mosq. Control Assoc. 20: 299-304, 2004) indicate that no individual values will be near zero. Using the rule of thumb that a distribution in which the mean is greater than three standard deviations above zero may be regarded as effectively normal, it is sensible to compute and report the normal 95% confidence interval in this study.

Employing eight subjects in a cage test, Cilek et al. (2004) recorded a mean protection time of approximately 180 minutes, with a standard error of about 15 minutes. Had their N been six, we can roughly predict that the 95% CI would be 148-212. At N=10, the estimate would be 155-205. At N= 20, the interval would be roughly 162-198. Evidently, adding the additional 10 subjects to reach an N of 20 shrinks the interval, in absolute terms, no more than did the addition of four subject to increase the sample size from 6 to 10.

To summarize, adding subjects beyond six increases the precision of the means estimate only slowly. However, the individual and public health importance of avoiding inaccuracy in this study, coupled with the fact that data collection is only 'replicated' once (in a different habitat at that), argues for a prudent approach. To reduce the risk of over-representing atypically attractive subjects, as well the weight of the value obtained from any one subject, we regard 10 (rather than six) treated subjects as a better sample size for the repellency portion of the study. For dosimetry, in contrast to repellency, less general information is available, and the risk profile is more benign. Consequently, a slightly larger sample is prudent. In meetings with EPA toxicology staff in 2005, 12 was regarded as an acceptably sample size for estimating mean dosage for each to the repellent formulations. Accordingly, we propose to employ a total of 12 subjects for dosimetry.

